## 7 STATISTICAL METHODOLOGY FOR SAFETY

The safety analysis for the secondary endpoints will be based on the “All Treated Patients” analysis set.

Patients will be evaluable for safety if they received at least one partial or complete infusion of PM01183.

### 7.1.1 *Toxicity and Adverse Events*

All the adverse events will be coded using the Medical Dictionary for Regulatory Activities (MedDRA).

The toxicity evaluation will be coded with the National Cancer Institute Common Terminology Criteria for Adverse Events (NCI-CTCAE), version 4.

As far as all the toxicities are concerned, the NCI-CTCAE grade will be used wherever an NCI-CTCAE grading exists. Otherwise, the severity will be noted. As a convention, the term «Grade» will always be used. Toxicities will be described according to the worst NCI-CTCAE grade or, for toxicities which do not form the subject of NCI-CTCAE classification, according to the worst severity.

Summary of overall AEs will be done by System Organ Class (SOC) and Preferred Term (PT), by severity (worst toxicity grade), by relationship to the study drug and by AE outcome. Tables will be sorted by SOC/PT coded with MedDRA.

A frequency table will be made for the AEs leading to cycle delay, dose reduction or withdrawal of study medication. Adverse events with outcome of death will also be presented by relationship to the study drugs.

### 7.2 *Clinical Laboratory Evaluation*

Laboratory results will be classified according to the NCI-CTCAE version 4.

The following hematological values (worst grade per patient and per cycle during treatment) will be displayed: white blood cells (WBC) count, neutrophil count, lymphocyte count, platelet count and hemoglobin.

Overall cross tabulation will be presented for the worst grade during treatment versus the baseline toxicity grading of anemia, lymphopenia, neutropenia, leukopenia and thrombocytopenia.

If a grade 3-4 neutropenia or thrombocytopenia increase occur during a cycle of treatment, the first day it reached the onset value (counting from the start of the cycle) and the duration of the abnormality (until recovery to grade  $\leq 2$ ), will be tabulated.

Similarly, the following biochemical values (worst grade per patient and per cycle during treatment) will be displayed: alanine aminotransferase (ALT), aspartate aminotransferase (AST), total bilirubin, alkaline phosphatase (AP), creatine phosphokinase (CPK),

creatinine, gamma-glutamyltransferase (GGT), calcium (corrected by albumin levels), potassium (K), sodium (NA), magnesium, glucose, phosphorus, triglycerides and albumin.

If a grade 3-4 AST or ALT increase occur during a cycle of treatment, both the day it peaked (counting from the start of the cycle) and the duration of the abnormality (until recovery to grade  $\leq 2$ ), will be tabulated.

Overall cross tabulation will be presented for the worst grade during treatment versus the baseline toxicity grading of biochemical abnormalities.

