Demographic data	-28 to 0	-	-	-	-	-	-	-
Primary diagnosis & prior treatment(s)	-28 to 0	-	-	-	-	-	-	-
Medical history & prior conditions	-14 to 0	-	-	-	-	-	-	-
Assessment of signs and symptoms	-7 to 0	-	-	-	-	-	-	-
PM01183 administration	NA	•	-	-	•	-	•	-
Complete physical examination, including weight and height⁽³⁾	-7 to 0	-	-	-	•	-	•	-
Performance status (ECOG)	-7 to 0	-	-	-	•	-	•	-
Vital signs (heart rate, blood pressure, temperature)	-7 to 0	-	-	-	•	-	•	-
Coagulation panel	-7 to 0	-	-	-	•	-	•	-
Hematology⁽⁴⁾	-7 to 0	-	•	•	•	•	• ⁽⁵⁾	•
Biochemistry A⁽⁴⁾	-7 to 0	-	•	•	•	•	• ⁽⁵⁾	•
Biochemistry B	-7 to 0	-	-	-	•	-	•	-
Pregnancy test⁽⁶⁾	-7 to 0	Repeat if clinically indicated						-
ECG⁽⁷⁾	-7 to 0	Repeat if clinically indicated						-
LVEF by ECHO or MUGA	-28 to 0	Repeat if clinically indicated						-
Radiological and/or clinical tumor assessment⁽⁸⁾	-28 to 0	Every 6 weeks until Cycle 6 and every 9 weeks thereafter ⁽⁹⁾						• ⁽¹⁰⁾
Pharmacokinetics (PK)⁽¹¹⁾	-	Immediately before and during Cycles 1 and 2 only.						-
PGx (paraffin embedded tumor tissue)⁽¹²⁾	From available prior tumor samples	-	-					
	From a recent biopsy (cohort A1)	After last treatment to 0	-					
Intercurrent events, concomitant diseases and treatments	-14 to 0	Throughout the "on-treatment period"						-
Adverse events (AEs)	NA ⁽¹³⁾	Throughout the "on-treatment period"						• ⁽¹³⁾
BRCA1/2 germline mutation analysis	• ⁽¹⁴⁾	BRCA unknown patients in cohort B: One blood sample at the time of the response ⁽¹⁵⁾						-

→ See footnotes on next page

Footnotes refer to table on previous page

1. A 3-day window will be allowed for laboratory procedures, a 14-day window for radiological procedures (helical CT-scan or MRI) and LVEF assessments, a 24-hour window for clinical assessments (ECOG, physical examination, vital signs, ECG, weight, BSA, etc.), and a 7-day window for the assessments at end of treatment.
2. After documented progression or start of new antitumor therapy, patients will be followed every six months, until death or study completion, whichever occurs first.
3. Height is only required at baseline.
4. **Any patient presenting a grade ≥ 3 treatment-related AE should have all relevant tests re-assessed at least every 48-72 hours until recovery to grade ≤ 2 .**

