5.2.2. Criteria for Treatment Continuation

Before the administration of each dose (re-treatment) on Day 1 of each cycle, patients must fulfill all of the criteria defined in [Table 2](#).

Table 2. Criteria for continuation of treatment.

Variable	Re-treatment
	Day 1
ECOG-PS	≤ 2
Hemoglobin*	≥ 8 g/dl
ANC	≥ 1.5 x 10 ⁹ /l
Platelets	≥ 75 x 10 ⁹ /l
AST/ALT	≤ 3.0 x ULN
Total bilirubin or direct bilirubin	≤ 1.5 x ULN or x ULN
Albumin	≥ 2.7 g/dl
Serum creatinine	≤ 2.0 x ULN
CPK	Grade ≤ 1
Other non-hematological drug-related AEs (except isolated increased GGT and/or AP [‡] , grade 3 asthenia lasting < 1 week, non-optimally treated nausea and/or vomiting)	Grade ≤ 2

* Patients may receive packed red blood cells (PRBC) transfusion and/or erythropoietin (EPO) treatment, if clinically indicated, to increase/maintain adequate hemoglobin levels.

[‡] Any grade accepted for non-drug-related increase of GGT and/or AP.

AE(s), adverse event(s); ANC, absolute neutrophil count; AP, alkaline phosphatase; AST/ALT, aspartate aminotransferase/alanine aminotransferase; CrCl, creatinine clearance; CPK, creatinine phosphokinase; ECOG, Eastern Cooperative Oncology Group; GGT, gamma-glutamyltransferase; PS, performance status; ULN, upper limit of normal.

If a patient does not meet the requirements for re-treatment on Day 1 of any following cycle, regardless of the reason, re-assessments will be performed every 48-72 hours. Treatment will be then withheld, up to a maximum of three weeks beyond its due date, until appropriate recovery.

Patients not meeting re-treatment criteria after a maximum three-week delay the patient must be withdrawn from the trial, except in case of objective clinical benefit (upon Sponsors' agreement).

For any delay lasting more than one week due to treatment-related toxicity (unless exclusively due to neutropenia), a dose reduction must be implemented upon recovery following the rules explained in the next section. Conversely, if the delay was exclusively due to neutropenia related to PM01183, treatment may continue without dose reduction but with appropriate secondary prophylaxis with granulocyte colony-stimulating factor (G-CSF).

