### **6.2.2 Secondary Endpoints**

Time-to-event endpoints (DR, PFS and OS) and their set time estimates (i.e. PFS3, PFS6 and 1y-OS) will be analyzed according to the Kaplan-Meier method.

A log-rank test or Cox regression for time-to-event endpoints could be performed as supportive analysis to compare both Cohorts.

If relevant, efficacy parameters versus baseline covariates will be analyzed and appropriate test will be used (i.e., the Fisher exact test and logistic regression for categorical variables, the log-rank test or Cox regression for time-to-event variables, etc.).

If appropriate, exploratory multivariate models (main effects or including interaction terms, if appropriate) will include all prognostic factors/covariates widely reported and recognized by oncologists: Cohort (BRCA (+) vs. BRCA (-) or unknown), BRCA (1 vs. 2 in cohorts A and A1), initial dose (7 mg FD vs 3.5 mg/m^2), age, age at diagnosis, race (Caucasian vs. other), baseline Eastern Cooperative Oncology Group performance status (ECOG PS) (0 vs. >0), histology type (Ductal vs. lobular carcinoma), histology grade (poorly vs. other), stage at diagnosis, primary tumor site (unilateral breast vs. bilateral), hormone receptor positive (estrogen or progesterone receptor +, or both +) vs. triple negative, HER-2 receptor (positive vs. negative), site of current disease such as liver metastases (yes vs. no), CNS metastases (yes vs. no), lung metastases (yes vs. no), non-visceral (including bone, skin, subcutaneous and lymph node vs. other), number of prior metastatic sites (1 vs. >1), body mass index (BMI), height, weight, body surface area (BSA), time from diagnosis to first infusion, prior surgery (yes vs. no), prior radiotherapy (yes vs. no), prior advanced treatment lines, prior advanced chemotherapy lines (0-1 vs. 2-3), prior anthracyclines (yes vs. no), prior taxane (yes vs. no), prior platinum (yes vs. no), prior PARPi (yes vs. no), last prior therapy PFS, first advanced chemotherapy PFS, last advanced chemotherapy PFS, PFS for anthracycline, taxane and platinum therapy, hormonotherapy (yes vs no), adjuvant/neoadjuvant therapy (yes vs no), platinum-free interval (in months), presence of any bulky (< 50 mm vs.  $\geq$  50 mm) lesion, albumin at baseline, CA-15.3 or 27.29 at baseline, any relevant concomitant medication at baseline (to be determinate by the oncologist) (yes vs. no) and the sum of all target lesion diameters.

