### ***8.8 Imputation of Incomplete Dates***

The dates of certain historical or current clinical activities are key component for statistical analysis. An incomplete date results from a missing day, month or year; in that case, the missing figure can be imputed allowing for the calculation of variables, such duration and time to certain event. However, when all of them, day, month and year, are missing no imputation will be done.

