### **8.10 Methods for Handling Missing Data**

Missing values will be tabulated with their frequency but they will not be included in the calculation of percentages.

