Table 12.4.4.13 Neutrophil count time course pattern (summary)

	Dose received						Total	
	7 mg FD / 3.5 mg/m 		6 mg FD / 2.6 mg/m 		5 mg FD/ 2.0 mg/m 			
	N	Median (range)	N	Median (range)	N	Median (range)		
G-CSF=Yes								
Baseline grade 0								
1 st cycle								
Onset day grade 4								
...								

	Dose received						Total	
	7 mg FD / 3.5 mg/m 		6 mg FD / 2.6 mg/m 		5 mg FD/ 2.0 mg/m 			
	N	Median (range)	N	Median (range)	N	Median (range)		
2 nd cycle, 3 rd cycle ....								
Onset day grade 4								
...								
	Total							
Onset day grade 4								
...								
Baseline grade 1, 2 ....								
...								
G-CSF=No								
...								
Total								
Total								
	1 st cycle							
Onset day grade 4								
...								
	2 nd cycle, 3 rd cycle ....							
Onset day grade 4								
...								
	Total							
Onset day grade 4								
Nadir day grade 4								
Nadir value grade 4								
Recovery day to grade $\leq 3$								
Duration in days to grade 3								
Recovery day to grade $\leq 2$								
Duration in days to grade 2								
Recovery day to grade $\leq 1$								
Duration in days to grade 1								

Table 12.4.4.14 Neutrophil count time course pattern (freqs)

	Dose received						Total	
	7 mg FD / 3.5 mg/m 		6 mg FD / 2.6 mg/m 		5 mg FD/ 2.0 mg/m 			
	N	%	N	%	N	%		
G-CSF=Yes								
Baseline grade 0								
	1 st cycle							
Onset day grade 4								
$\leq 7$								
8-14								
$\geq 15$								
...								
	2 nd cycle, 3 rd cycle ....							
Onset day grade 4								
$\leq 7$								
8-14								
$\geq 15$								
...								
	Total							
Onset day grade 4								
$\leq 7$								
8-14								
$\geq 15$								

	Dose received						Total	
	7 mg FD / 3.5 mg/m 		6 mg FD / 2.6 mg/m 		5 mg FD/ 2.0 mg/m 			
	N	%	N	%	N	%	N	%
...								
Baseline grade 1, 2 ....								
...								
G-CSF=No								
...								
Total								
Total								
	1 st cycle							
Onset day grade 4								
≤ 7								
8-14								
≥ 15								
...								
	2 nd cycle, 3 rd cycle ....							
Onset day grade 4								
≤ 7								
8-14								
≥ 15								
...								
	Total							
Onset day grade 4								

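### SAP 7.2 gives no rule for grade 3–4 laboratory episodes without observed recovery, and the natural reading shortens the reported durations

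*SAP*

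**What the plan says.** SAP 7.2 (Clinical Laboratory Evaluation) sets the rule for blood counts. For grade 3–4 neutropenia or thrombocytopenia it tabulates "the first day it reached the onset value (counting from the start of the cycle) and the duration of the abnormality", with recovery to grade 2 or lower as the end point. For grade 3–4 AST or ALT it tabulates "both the day it peaked (counting from the start of the cycle) and the duration of the abnormality (until recovery to grade" 2 or lower). Neither sentence covers an episode with no observed recovery.

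Four other parts of the SAP bear on such an episode:

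- **SAP 8.10:** "Missing values will be tabulated with their frequency but they will not be included in the calculation of percentages".
- **SAP 8.8**, on dates: "when all of them, day, month and year, are missing no imputation will be done".
- **SAP 6.2.2** assigns the Kaplan-Meier method to "Time-to-event endpoints (DR, PFS and OS) and their set time estimates". Laboratory durations are not listed.
- **SAP 12.4.4**, Tables 12.4.4.11 to 12.4.4.18, has rows such as "Duration in days to grade 2". They are shown as N with median and range, or as N and % in the bands ≤5, 6–10 and ≥11 days. The shells that can be read have no row for censored or unrecovered episodes.

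The protocol limits how often recovery goes unseen. In the schedule of assessments (footnote 4), a patient with a treatment-related event of grade 3 or higher "should have all relevant tests re-assessed at least every 48-72 hours until recovery to grade" 2 or lower. If re-treatment criteria are not met, Protocol 5.2.2 says: "Treatment will be then withheld, up to a maximum of three weeks beyond its due date, until appropriate recovery". Protocol 6.7 repeats laboratory work at the end-of-treatment visit if the last result was grade 2 or higher.

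**The concern.** Duration to recovery is a time-to-event quantity. An episode that is still open at death, at the start of another therapy, at withdrawal or at the last blood test is right-censored: its duration is known only to exceed the time observed. A summary of completed episodes alone therefore understates duration.

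What is at stake is a descriptive safety statement. Both documents describe the drug's neutropenia as short-lasting, and Protocol 1.2.1.2 gives a phase I median of three days for grade 4 neutropenia at the recommended dose. The time-course tables are where that description is checked in this trial. Protocol 5.2.2 also requires withdrawal of patients who still fail re-treatment criteria after a three-week delay, unless there is objective clinical benefit. Prolonged non-recovery can thus itself end treatment, and those are episodes the tables need to show.

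**Working it through.** The documents give no figure for laboratory durations in this trial, so there is nothing to reproduce. The check has two parts: what the rules do to an unrecovered episode, and how much that could matter.

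**1. Tracing an unrecovered episode through the rules**

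- It has an onset day and a grade, so it appears in the onset rows and the worst-grade tables.
- It has no recovery date. SAP 8.8 does not create one, so it has no duration under SAP 7.2.
- It cannot enter a median that has no censoring method, and SAP 6.2.2 does not extend Kaplan-Meier to these tables.
- In the banded tables, if treated as missing, it leaves the denominator under SAP 8.10 and is shown only as a missing count.

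If a programmer instead closed the episode at its last test, the recorded value would be a lower bound on the duration, which is also too short. The text rules out neither choice.

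**2. Effect on the percentages**

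Let R be the recovered episodes, U the unrecovered ones, and u = U/(R+U). A band holding k recovered episodes is reported as k/R instead of k/(R+U), so it is inflated by 1/(1−u): 1/0.95 = 1.05 at u = 5%, 1/0.90 = 1.11 at 10%, and 1/0.80 = 1.25 at 20%. With unrecovered episodes kept in the denominator, the share lasting 11 days or more is bounded between k/(R+U), with k now the ≥11-day band, and (k+U)/(R+U).

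**3. Effect on the median (illustration)**

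Inputs: true median M = 3 days (Protocol 1.2.1.2, phase I, grade 4 neutropenia only). The exponential shape and u are assumptions; the documents give no unrecovered share.

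- (a) Unrecovered episodes are the longest: recovered-only median = −ln(1 − 0.5(1−u)) × M/ln 2.
- (b) Censoring is independent of duration and exponential: recovered-only median = M(1−u).

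At u = 5%: (a) −ln(0.525) × 3/0.693 = 2.79 days; (b) 3 × 0.95 = 2.85 days.

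The true share lasting 11 days or more is exp(−11 ln 2/3) = 7.9%. At u = 5% the recovered-only share is (a) (0.079 − 0.05)/0.95 = 3.0% and (b) exp(−11 ln 2/(3 × 0.95)) = 6.9%.

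| u (assumed) | Recovered-only median, (a) to (b), days | Shortening | Recovered-only share ≥11 days, (a) to (b) |
|---|---|---|---|
| 0% | 3.00 | none | 7.9% |
| 5% | 2.79 to 2.85 | 5–7% | 3.0% to 6.9% |
| 10% | 2.59 to 2.70 | 10–14% | 0% to 5.9% |
| 20% | 2.21 to 2.40 | 20–26% | 0% to 4.2% |

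Both median formulas are proportional to M, so the percentage shortening is the same for true medians of 5 or 7 days. Under (b), a Kaplan-Meier median simulated with 20,000 episodes stayed at 2.96–3.01 days for u from 0% to 30%. Case (b) also shows that the shortening does not require the unrecovered episodes to be the longest ones.

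**The case against.** The strongest reply is that the SAP never says unrecovered episodes are excluded, and that they would not be hidden. A reader might infer that these episodes vanish from the report, but the documents do not support that. SAP 8.10 requires the frequency of missing values to be tabulated. The shells carry separate Ns for onset, recovery and duration, so a shortfall would show. The episodes also stay in the worst-grade tables and grade 3–4 listings. This stands: exclusion is an inference from silence, and the number would be visible. But a displayed missing count corrects neither the percentages nor the median beside it.

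Second, the protocol's retesting, dose-hold and end-of-treatment rules should leave few unrecovered episodes, mainly in a patient's last cycle. This also stands, with limits. The retesting rule is tied to treatment-related adverse events, and Protocol 11.2.1 records a laboratory abnormality as one only under certain conditions, so an asymptomatic grade 3 count may fall outside it. None of the three rules reaches an episode cut short by death, a new therapy or withdrawal of consent.

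Third, recovery is dated by the next blood test, which lengthens recorded durations. That is fair as a caution about net error. Onset is also dated by a test, which works the other way. Neither is a reason to omit unrecovered episodes; the direction claimed here is that of the omission alone.

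Fourth, pooled Kaplan-Meier is not clean, because episodes recur within patients and death competes with recovery. This stands, and is why Kaplan-Meier is optional in the fix.

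**Conclusion.** The point holds as a gap in SAP 7.2. Duration ends only at recovery, no rule covers episodes without it, and the natural reading leaves them out of the duration medians and banded percentages while showing their number as missing. The omission shortens reported durations. Its size cannot be fixed from the documents. It is zero if every episode is seen to recover, 5–7% of the median if 5% are not, and 10–14% if 10% are not, under the exponential assumption. Given the protocol's safeguards, it is probably small.

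A reader might be tempted to count the omitted episodes by applying the phase I rate of 40% grade 4 neutropenia to the roughly 110 patients expected. The documents do not support that. The rate comes from 15 patients at the recommended dose (0.40 × 15 = 6). Part of this trial starts at 3.5 mg/m² instead of the 7 mg flat dose. The time-course tables are broken down by cycle, so patients are not episodes. No unrecovered share is stated anywhere.

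These are descriptive safety tables. The primary analysis of response rate and the safety stopping rule in Protocol 8.3.3 are unaffected. This is a cheap improvement, not a flaw in the trial's conclusions.

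**What to change.** In SAP 7.2 and Tables 12.4.4.11 to 12.4.4.18:

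- Define an episode without observed recovery, and add a row for *not recovered at last available test*. Keep it in the denominator of the recovery-day and duration percentages.
- State that these rows are exempt from the exclusion in SAP 8.10.
- Label the medians as based on recovered episodes. Alternatively, report Kaplan-Meier medians with unrecovered episodes censored at the last test, noting that patients can contribute repeated episodes and that death is a competing event.
- In the same edit, reconcile the scope: SAP 7.2 speaks of grade 3–4 neutropenia and thrombocytopenia, while the platelet and neutrophil shells start at onset of grade 4.

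The cost is a little programming and one extra row per table, with no new data. The duration figures may look slightly less favourable.

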### ***7.3 Vital Signs, Physical Examination, Left Ventricular Ejection Fraction and Electrocardiogram Findings***

Tabulation will be made summarizing the performance status, body weight, left ventricular ejection fraction (LVEF) and electrocardiogram (ECG) abnormalities at baseline and during the treatment, if appropriate, for each patient.

### ***7.4 Deaths and Other Serious Adverse Events***

Deaths and other SAEs will be tabulated.

## **8 OTHER ANALYSIS**

Continuous variables will be tabulated and presented with summary statistics (i.e., median and range).

Categorical variables will be summarized in frequency tables by means of counts and percentages. Percentages in the summary tables will be rounded and may therefore not always add up to exactly 100%.

### ***8.1 Patient Disposition and Treatment/Study Discontinuation***

The number of patients included in the study, the number of patients treated and the number of patients evaluable for the main endpoint, will be shown. Also, accrual by center and country and the main dates of the study will be displayed. Reasons for treatment discontinuation and for study discontinuation will be tabulated.

### ***8.2 Protocol Deviations***

Analysis of inclusion/exclusion criteria deviations, retreatment restrictions, concomitant medication and clinically relevant discontinuations, among others, will be done as described in Appendix I.

### ***8.3 Baseline and Demographic Data***

Baseline data such as demographics, cancer history, prior therapy, prior relevant history, signs and symptoms, electrocardiogram, LVEF, physical examination, vital signs, laboratory values and concomitant medication, coded according to the World Health Organization (WHO) Anatomical Therapeutic Chemical (ATC) classification system, will be described following standard tables detailed in Appendix I.

Age, baseline weight, height, and body surface area (BSA) will be summarized descriptively.

Age will be calculated based on the date of birth and the date of informed consent.

Baseline weight and height are recorded on the CRF.

Baseline BSA will be calculated using the Dubois & Dubois formula:

$$BSA(m^2) = 0.007184 \times weight(kg)^{0.425} \times height(cm)^{0.725}$$

Age categories and race will be summarized with frequency counts.

Baseline Eastern Cooperative Oncology Group (ECOG) performance status (PS) will be summarized with frequency counts.

For the cancer history: time from initial diagnosis, time from metastatic disease and time from last progression before the study entry will be summarized. This time calculations will be shown in months and summarized descriptively. Histology and characteristics of the current disease will be tabulated.

Previous relevant medical history (other than cancer) will be listed.

A frequency tabulation of the number of patients with and the different types of previous surgery, radiotherapy, or therapy (number of lines) will be given.

Signs and symptoms at baseline will be displayed by tabulation of frequencies according to NCI-CTCAE version 4 toxicity grades. Signs and symptoms will be listed.

In case of pre-treatment characteristics with multiple measurements per subject before the start of treatment (laboratory assessments, vital signs) the baseline measurement will be considered the last value prior to or on the first day of treatment.

Baseline and demography characteristics in different subgroups of analysis (i.e. cohorts) will be compared by means of Fisher's exact test (categorical variables) and Mann-Whitney-Wilcoxon (continuous variables).

